## 1. INTRODUCTION

This RAP is intended to describe planned safety, tolerability, pharmacokinetics (PK), and efficacy analyses to be performed in support of the Clinical Study Report for GSK Protocol 207675 Amendment 3, dated 05DEC2019.

| Protocol Revision Chronology: |             |   |
|--------------------------------------|-------------|---|
| Version 01                           | 02-MAY-2018 | Original  |
| Version 02
(Amendment 1)          | 12-JUL-2018 | Changed included: 
 
- Modified DLT definitions.
 
- Changes to inclusion criteria.
 
- Incorporation of a hold of study drug for most related Grade 3 adverse events with possible re-start at reduced dose level for thrombocytopenia, anemia, diarrhea, nausea/vomiting, and all other non-hematologic toxicities.
 
- Incorporation of discontinuation of study drug for related Grade 4 adverse events of any duration (excluding most lab abnormalities).
 
   |
| Version 03
(Amendment 2)          | 22-FEB-2019 | Changes included: 
 
- Changes and clarifications made in the Schedule of Activities Tables.
 
- Update to CTCAE version 5.
 
- Minor change to inclusion and exclusion criteria
 
 Addition of higher dose strength capsules   |
| Version 04
(Amendment 3)          | 05-DEC-2019 | Changes included: 
 
- Updated clinical safety guidelines, clinical pharmacology, and the risks/mitigation strategy following the temporary pause in enrolment due to venous thromboembolic events (VTE) that have been observed in the dose escalation phase of the study. Also, the risk of biopsy collection has been added to the benefit/risk assessment table.
 
- Changes to exclusion criteria.
 
- Addition to allowed anti-coagulation therapy.
 
- Addition of exploratory coagulation markers and minor changes to other exploratory biomarkers being collected in the dose escalation phase of the study (Part 1).
 
- Changes and clarifications made in the Schedule of Activities Tables
 
- Changes to DLT and stopping/exclusion criteria for QRS and VTEs, and update to the telemetry assessment.
 
- Addition of food effect cohort into Part 1.
 
- Addition of tablet formulation.
 
 |

|  |  |  |
|--|--|--|
|  |  | 
 
- Further clarifications added to the sample size determination section.
 
- Addition of albumin in the clinical labs table (Table 9, Appendix 2).
 
- Addition of guidelines of management of toxicity for VTEs in Appendix 12
 
- Addition of Appendix 13 (Khorana score)
 
- Administrative changes made throughout the document.
 
 |
|--|--|--|

## 2. SUMMARY OF KEY PROTOCOL INFORMATION

### 2.1. Changes to the Protocol Defined Statistical Analysis Plan

The Dose Escalation Committee (DEC) evaluated the DL100mg cohort and deemed it safe, but upon review of the cumulative safety, efficacy, PK and PD data, GSK decided that no further enrolment will take place on the study. As a result, all analyses corresponding to Part 2, as well as the Exploratory Objectives for both Part 1 and Part 2, will not be performed. Below is the list of analyses that will not be performed:

- There will be no food effect sub-study analysis. Therefore, one of the secondary objectives from Part 1 analysis will not be performed.
- There will be no Part 2 Dose Expansion cohort. Thus, all analyses which support characterization of primary and secondary objectives for the Part 2 cohort (objective response rate analysis, progression-free survival incidence, severity of adverse events, and evaluation of PK parameters) will not be performed.
- Recommended Phase 2 Dose (RP2D) Analysis will not be performed.
- Interim futility analysis (IFA) will not be performed.

### 2.2. Study Objective(s) and Endpoint(s)

[figure not shown]
| Objectives   | Endpoints  |
|--|--|
| Part 1: Dose Escalation   |  |
| Primary Objective   | Primary Endpoints   |
| 
 
• Determine RP2D and schedule of GSK3368715 administered orally to participants with advanced stage solid tumors
 
 | 
 
• Incidence of DLT
 
• Incidence and severity of adverse events
 
 |
| Secondary Objectives  | Secondary Endpoints   |
| 
 
• Evaluate the preliminary clinical activity of GSK3368715
 
   | 
 
• Best overall response
 
  |
| 
 
• Characterize the PK of GSK3368715
 
  | 
 
• PK parameters (Cmax, Tmax, AUC, and others)
 
                          |
| Part 2: Dose Expansion  |  |
| Primary Objective   | Primary Endpoint  |
| 
 
• Evaluate the preliminary clinical activity of GSK3368715
 
   | 
 
• Objective response rate (ORR)
 
  |

| Secondary Objectives  | Secondary Endpoints   |
|---|---|
| 
 
Characterize the safety of GSK3368715 administered at the RP2D and schedule to participants with DLBCL, pancreatic cancer, NSCLC, and bladder cancer
 
                  | 
 
Incidence and severity of adverse events
 
                          |
| 
 
Further evaluate the clinical activity of GSK3368715
 
  | 
 
Progression-free survival (PFS)
 
                                   |
| 
 
Characterize the PK of GSK3368715
 
   | 
 
PK parameters (Cmax, Tmax, AUC, and others)
 
 |
| Part 1 and Part 2  |   |
| Exploratory Objectives/Endpoints   |   |
| 
 
Evaluate time to response (TTR), duration of response (DOR) and overall survival (OS)
 
   |   |
| 
 
Evaluate changes in PD biomarkers relevant to define the molecular mode-of action of GSK3368715
 
   |   |
| 
 
Investigate biomarkers such as, but not restricted to, MTAP deficiency and CDKN2A gene deletion, as potentially predictive of sensitivity or resistance to GSK3368715
 
 |   |
| 
 
Characterize the relationship between PK, PD, and clinical activity of GSK3368715
 
   |   |
| 
 
Evaluate the relationship of pharmacogenetic profile in host DNA and response to GSK3368715 therapy
 
   |   |
| 
 
Determine the impact of GSK3368715 on function and health-related quality of life
 
   |   |
| 
 
Determine the amount of GSK3368715 excreted in urine from subjects in the PK/PD expansion cohorts
 
   |   |
| 
 
Characterize the metabolic profile of GSK3368715 (in the PK/PD expansion cohorts)
 
   |   |

## 2.3. Study Design

### Overview of Study Design and Key Features

- Participants with advanced/refractory solid tumors.
- Under protocol amendment 03, enrollment will resume in the 100 mg PK/PD cohort and the 50 mg PK/PD cohort.
- Dose escalation will be limited to 50 mg increments.

|                               |  |
|-------------------------------|--|
| 
Design Features
 | 
 
The study includes two phases: Part 1 Dose Escalation and Part 2 Dose Expansion.
 
Dose escalation use Neuenschwander continual reassessment method (N-CRM).
 
Cohorts will be expanded at the first instance of a <math>\geq</math> Grade 2 drug-related non-hematological toxicity.
 
Every dose level will enroll a minimum of 3 and a maximum of 12 subjects.
 
Part 1 was planned to enroll up to 40 patients with relapsed/refractory solid tumors. Approx. 30 subjects for DLT evaluation and 10 subjects for PK/PD/Biomarker cohort(s) at a dose of or near MTD/RP2D.
 
Dose Escalation Committee (DEC):                     
 
will review all available data, including safety, PK and PD data from current and prior cohorts,
 
can halt or reduce the GSK3368715 dose based on clinical judgement at any time during the trial, and
 
can recommend alternative schedule(s) if emerging data suggest that continuous daily dosing will result in excessive toxicity or limited efficacy.
 
                     Refer to Section 4.1.4 in protocol for the detailed descriptions of the DEC.                 
 
Maximum-tolerated Dose (MTD): The highest GSK3368715 dose that emerges from the evaluation of safety-, PK-, and PD-data guided by the N-CRM statistical design during the DLT evaluation period that does not produce unacceptable toxicity.
 
Recommended Phase 2 Dose (RP2D): Equivalent with the MTD or a lower GSK3368715 dose that provides adequate PK exposure and biologic activity with superior tolerability.
 
 |
|-------------------------------|--|

| Overview of Study Design and Key Features |  |
|--|--|
|  | 
 
Part 2 was planned to enroll up to 141 patients. Specifically, Cohort 2A was planned to enroll up to 36 DLBCL participants. Cohort 2B was planned to enroll up to 35 participants for each indication of pancreatic cancer, NSCLC, and bladder cancer.
 
In both expansion cohorts, MTAP proficient and deficient participants were to be enrolled.
 
Participants may continue treatment in the study until disease progression, unacceptable toxicity, or withdrawal of consent.
 
   |
| Dosing                                    | 
 
The starting dose of GSK3368715 is 50 mg, qd, po.
 
At the time of each dose-escalation decision, the dose that has the highest posterior probability of DLT lying in the target toxicity range (<math>\geq 16\%</math> and <math>< 33\%</math>) with the constraint of posterior probability falling to unacceptable/excessive toxicity being less than 25% will be the model-recommended dose for the next cohort.
 
The dose will not increase by more than half-logarithmical (3.2-fold) increments.
 
Dose de-escalation is also possible.
 
Based on the emerging data, alternative dosing schedule(s), or combination regimens with novel, active agents and/or with approved oncology therapies may be considered.
 
Any cohort in Part 1 with two (2) grade 2 venous thromboembolism (VTE) that requires systemic anticoagulation or <math>\geq</math> grade 3 VTE in up to 6 participants will be considered not cleared and enrolment at this dose level and higher dose levels will be permanently stopped.
 
Any cohort in Part 1 with <math>\geq 3</math> grade 2 venous thromboembolism (VTE) that requires systemic anticoagulation or Grade <math>\geq 3</math> VTEs out of up to 10 participants will be considered not cleared and enrolment at this dose level and higher dose levels will be permanently stopped.
 
At 100mg, dose escalation steps will be considered in maximal steps of 50 mg depending on the pharmacodynamic effects and the safety profile observed in previous cohorts, taking into consideration the updated DLT criteria.
 
Grade 2 venous thromboembolism (VTE) that requires systemic anticoagulation or <math>\geq</math> grade 3 VTE, regardless of investigator assessed causality, will be considered a DLT during the first 8 (<math>\pm 1</math>) weeks or until study discontinuation (e.g., disease progression), whichever occurs sooner.
 
An end of treatment CT image is required if the participant withdraws before the end of the VTE DLT observation period.
 
 |
| Time & Events                         | 
 
Refer to Table 2: Schedule of Assessments (SoA) in protocol
 
  |
| Treatment Assignment                      | 
 
The study is open-label and GSK3368715 is the only treatment assignment.
 
   |
| Interim Analysis                          | 
 
The interim analysis was planned to be conducted separately for Cohorts 2A and 2B.
 
Timing of the first interim futility analysis:
Cohort 2A: When at least 5 participants become evaluable from each of the MTAP defined subgroups.
 
   |

| Overview of Study Design and Key Features |   |
|--|---|
|  | 
Cohort 2B: When at least 5 participants become evaluable from MTAP proficient subgroup within any histology cohort.
 
 
• The interim futility analysis was planned to be performed every 2-3 months with minimum of 5 additional evaluable participants from the entire Cohort 2A or Cohort 2B.
 
• Within Cohort 2A, one Bayesian hierarchical model was to be used to borrow information between the MTAP defined subgroups. Within Cohort 2B, one Bayesian hierarchical model was to be used to borrow information between the MTAP defined subgroups and between the three indications.
 
• Participants enrolled in Part 1 who were treated at the RP2D of GSK3368715 and have the same disease histology as required for Expansion Cohort 2B were to be included in the analyses as appropriate.
 
• The above interim analyses will no longer be carried out due to the early termination of the study.
 
 |
| Final Analysis                            | 
 
• The study will be considered completed for purposes of a final analysis when 70% of participants enrolled in Part 2 have progressed or died. Due to the early termination during the Dose Escalation (Part 1) phase of this study, final analysis will occur prior to the above definition.
 
   |

## **2.4. Statistical Hypotheses / Statistical Analyses**

### **2.4.1. Part 1 Dose Escalation**

No specific statistical hypotheses are being tested in Part 1. The primary objective is to determine RP2D.

### **2.4.2. Part 2 Dose Expansion**

The Dose Escalation Committee (DEC) evaluated the DL100mg cohort and deemed it safe, but upon review of the cumulative safety, efficacy, PK and PD data, GSK decided that no further enrolment will take place on the study. As a result, all analyses corresponding to Part 2, as well as the Exploratory Objectives for both Part 1 and Part 2, will not be performed. However, all other Part 1 analyses will be performed.

### 3. PLANNED ANALYSES

#### 3.1. Interim Analyses

In Part 1, dose escalation meetings will be held to discuss dose escalation decisions after all patients in each dose cohort complete the DLT evaluation period of the first 21 days of intervention. Once all subjects in the DLT evaluation cohort (approx. 30 in total) have completed the first post baseline disease assessment, progressed or permanently discontinued from study treatment, a RP2D analysis will be conducted.

The Dose Escalation Committee (DEC) evaluated the DL100mg cohort and deemed it safe, but upon review of the cumulative safety, efficacy, PK and PD data, GSK decided that no further enrolment will take place on the study. As a result, all analyses corresponding to Part 2, as well as the Exploratory Objectives for both Part 1 and Part 2, will not be performed. However, all other Part 1 analyses will be performed.

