Number of Participants: It is estimated that up to approximately 60 participants will be enrolled in Part 1. In Part 2, approximately 141 participants will be recruited into Expansion Cohort 2A (~36 participants) and Expansion Cohort 2B (~ 105 participants). Additional tumor-specific cohort(s) and combinations may be added by protocol amendment, based upon emerging pre-clinical data, or clinical data.

Intervention Groups and Duration: In Part 1 of the study, the participants will initially receive GSK3368715 orally. This will include at least one PK/PD cohort and a food effect cohort. The Dose Limiting Toxicity (DLT) period is 21 days, and under protocol amendment 3, there is an addition of a VTE-specific DLT period of 8 (\pm 1) weeks or until study discontinuation whichever occurs sooner. An end of treatment CT image is required if the participant withdraws before the end of the DLT observation period. Alternative dosing schedules and intervention cycles may be investigated. In Part 2, the participants are expected to receive the RP2D established in Part 1. In case of unexpected toxicities, alternative GSK3368715 doses may be explored in Part 2.

The study includes a screening period, an intervention period and follow up. Participants will be screened for eligibility beginning approximately 4 weeks before the start of intervention. Participants with confirmed partial response (PR) or complete response (CR) will be followed for response duration and may be eligible for additional intervention with GSK3368715 at the time of relapse/progression if determined to be deriving clinical benefit in the opinion of the investigator and with approval from the study Medical Monitor.

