Thromboembolic Risk	A higher than expected incidence of venous thromboembolism was observed in the first 19 participants treated on clinical study 207675.	
 • Change in inclusion/exclusion criteria, to exclude participants at high risk of VTE. • Extended monitoring time for VTE events to clear dose prior to dose escalation. • Include cohort stopping rules for VTE • Resume enrollment under protocol amendment 03 at reduced dose of 100 mg po daily • Limit dose escalation to 50 mg increments.
Study procedures		
Biopsy	A tissue biopsy is required in PK/PD cohorts to evaluate tumor expression of the biomarkers pathway. Risks associated with a tumor biopsy depend upon the location and type of biopsy performed. Pain, infection, bleeding may occur after the procedure. Additional risks depending on the location of the biopsy may include pneumothorax, pneumonia, injury to surrounding nerves or organs, hospitalization, and, rarely, death.	
 • Participants will be informed of the specific risks associated with the biopsy to be performed through the ICF. Participants at increased risk or not well suited to undergo a biopsy should not be enrolled in a cohort that requires a fresh biopsy. Participants will be treated according to local practice.

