4.1.1. Part 1: Dose-Escalation Phase

Cohort Size: The initial dose cohort(s) will include up to three participants per GSK3368715 dose level. Cohorts will be expanded at the first instance of a \geq Grade 2 drug-related non-hematological toxicity. From there on, a minimum of 3 and a maximum of 12 DLT evaluable participants may be assigned to any single dose at the discretion of the Dose Escalation Committee (DEC) as outlined in the Dose Escalation Plan.

Replacement: If a participant fails to receive at least 75% of the planned doses within the 21-day DLT observation period for reasons other than toxicity (e.g., concurrent illness or disease progression), the participant will be replaced by additional participant(s) assigned to the same dose level and will not be counted as DLT evaluable.

Dose Escalation: After each dose cohort, a dosing recommendation for the next cohort will be made using the Neuenschwander Continual Reassessment Method (N-CRM) [[Neuenschwander, 2008](#)].

The N-CRM design makes use of a Bayesian logistic regression model relating dose and toxicity and is expected to locate the target dose level efficiently while minimizing the number of participants exposed to pharmacologically inactive or unsafe dose levels. The N-CRM method is fully adaptive and makes use of all DLT information, therefore is expected to locate the target dose level efficiently.

The N-CRM estimates, for each potential dose, the posterior probabilities that the DLT rate lies in each of four toxicity ranges:

- A dose falls in the **Under-dosing** range if the probability of a DLT at the dose is, 16%.
- A dose falls in the **Target** Toxicity range if the probability of a DLT at the dose is $\geq 16\%$ and $< 33\%$.
- A dose falls in the **Excessive** Toxicity range if the probability of a DLT at the dose is $\geq 33\%$, and $< 60\%$.
- A dose falls in the **Unacceptable** Toxicity range if the probability of a DLT at the dose is $\geq 60\%$

At the time of each dose-escalation decision, the dose with the highest posterior probability of lying in the Target Toxicity range will be the model-recommended dose for

the next cohort. Additionally, the following constraints for the recommended dose will be maintained:

- The posterior probability of the DLT rate lying in the Excessive Toxicity or Unacceptable Toxicity range is less than 25%.
- VTE safety rules

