4.1.3. Dose-Limiting Toxicity

All toxicities will be graded using National Cancer Institute – Common Toxicity Criteria for Adverse Events (NCI-CTCAE), version 5.

An AE is considered to be a dose-limiting toxicity (DLT) if the event is considered by the investigator to be clinically relevant and attributed (definitely, probably or possibly) to the study intervention during the first 21 days of intervention and meets at least one of the criteria listed in [Table 6](#).

In addition, there are clear VTE DLT criteria:

- Upon re-initiation of enrolment under Protocol Amendment 3, any cohort in Part 1 with two (2) grade 2 venous thromboembolism (VTE) that requires systemic anticoagulation or \geq grade 3 VTE in up to 6 participants will be considered not cleared and enrolment at this dose level and higher dose levels will be permanently stopped.
- Upon re-initiation of enrolment under Protocol Amendment 3, any cohort in Part 1 with ≥ 3 grade 2 venous thromboembolism (VTE) that requires systemic anticoagulation or Grade ≥ 3 VTEs out of up to 10 participants will be considered not cleared and enrolment at this dose level and higher dose levels will be permanently stopped.
- Upon re-initiation of enrolment under Protocol Amendment 3 at 100mg, dose escalation steps will be considered in maximal steps of 50 mg depending on the pharmacodynamic effects and the safety profile observed in previous cohorts, taking into consideration the updated DLT criteria (see [Table 6](#)).
- Grade 2 venous thromboembolism (VTE) that requires systemic anticoagulation or \geq grade 3 VTE, regardless of investigator assessed causality, will be considered a DLT during the first 8 (± 1) weeks or until study discontinuation (e.g., disease progression), whichever occurs sooner.
- An end of treatment CT image is required if the participant withdraws before the end of the VTE DLT observation period ([Table 6](#)).

If an AE is considered related to the underlying disease it is not defined as a DLT.

Table 6 Dose-Limiting Toxicity Criteria

DLT criteria for Non-hematologic Toxicity	
AST or ALT	
 • Grade 3 • Grade 4 • ALT \geq 5xULN • ALT \geq 3xULN persists for \geq 4 weeks • ALT \geq 3xULN and bilirubin \geq 2xULN (>35% direct bilirubin) • ALT \geq 3xULN and INR >1.5, if INR measured • ALT \geq 3xULN associated with symptoms (new or worsening) believed to be related to liver injury or hypersensitivity

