Nausea	
 • Grade 3 persisting >3 days despite BSC^a
Vomiting	
 • Grade 3 or 4 persisting > 3 days despite BSC^a
Diarrhea	
 • Grade 3 or 4 persisting > 3 days despite BSC^a
Fatigue	
 • Grade 3 persisting > 5 days
Hypertension	
 • Grade 3 that cannot be controlled with medical therapy • Grade 4
ECG-change	
 • > 20 msec extension of the QRS-interval compared to baseline
Laboratory abnormality	
 • Grade 3 persisting > 3 days despite BSC^a • Grade 4
Any other	
 • Grade 2 leading to frequent dose interruptions despite BSC^a and limiting GSK3368715 dosing to <80% of expected dose • Grade 2 requiring delay of GSK3368715 administration for > 14 days • Grade \geq3

DLT criteria for Hematologic Toxicity	
Neutropenia	
 Grade 3 persisting > 3 days despite BSC^a Febrile neutropenia Grade 4
Thrombocytopenia	
 Grade 3 persisting > 3 days despite BSC^a Grade 3 associated with clinically significant hemorrhage Grade 4
Any other ^b	
 Grade 2 and 3 leading to frequent dose interruptions despite BSC^a and limiting GSK3368715 dosing to < 80% of expected dose Grade 3 persisting > 3 days despite BSC^a Grade 4
Venous Thromboembolism	
 Grade 2 venous thromboembolism (VTE) that requires systemic anticoagulation or VTE Grade ≥ 3 during the first 8 (± 1) weeks or until study discontinuation (e.g., disease progression), whichever occurs sooner.

ALT=alanine aminotransferase; AST=aspartate aminotransferase; BSC=best supportive care; DLT=dose-limiting toxicity; ECG=electrocardiogram; ULN=upper limit of normal

- a. Best supportive care if available, according to institutional standards
b. With the exception of lymphocytopenia

For participants who experience a toxicity that meets the criteria of DLT, administration of GSK3368715 will be held pending management and resolution of the toxicity.

Participants who withdraw from the study before completing 21 days of intervention for reasons other than DLT may be replaced at the discretion of the sponsor.

Guidance for the management of toxicity, including dose modification algorithms, is provided in [Appendix 12](#).

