4.1.4. Dose Escalation Committee

The Dose Escalation Committee (DEC) will be established by GSK to monitor intervention-emergent data on an ongoing basis throughout study conduct for the purpose of ensuring the continued safety of participants enrolled in this study. The DEC will be chaired by the GSK medical monitor and membership will include a GSK scientist, GSK pharmacovigilance physician, GSK statistician, GSK pharmacologist, along with additional GSK staff as appropriate and all participating investigators.

In Part 1, the DEC will review relevant safety, PK, and PD data generated immediately after all participants treated in the same dose cohort have passed the DLT period, as defined in the Dose Escalation Plan. Although the escalation of the GSK3368715 dose will be guided by the N-CRM, the DEC can override this recommendation.

In Part 2, the members from the DEC will continue to routinely assess cumulative safety data as a safety evaluation team. This team may decide to stop further enrolment if intervention-emergent toxicity is determined to result in an unfavourable change in participant risk/benefit.

In addition, throughout the conduct of the study the DEC may decide to:

1. Modify the dose escalation of GSK3368715 proposed by the N-CRM based on clinical judgement. *Note:* GSK3368715 dose steps will not exceed 50 mg dose increments under protocol amendment 03.
2. Investigate alternative dosing regimens
3. Modify the timing, frequency, and/or type of safety assessments performed during study conduct
4. Request intervention of additional participants at previously completed dose levels for the purpose of obtaining additional safety, PK, PD, metabolite, or biomarker data (i.e. PK/PD/Metabolite/Biomarker-Cohort).
5. Recommend intra-participant dose escalation allowing participants to be moved from a lower to a higher GSK3368715 dose, not exceeding the MTD if the DEC has declared the next dose cohort as safe
6. Decide on intervention beyond initial evidence of disease progression in participants who receive clinical benefit (i.e., stable Eastern Cooperative Oncology Group or ECOG performance status and no clinical symptoms indicative of rapid disease progression)
7. Increase the size of an expansion cohort or recommend to add additional expansion cohorts to further characterize the safety and efficacy profile of GSK3368715
8. Halt enrolment into any cohorts as deemed appropriate based on emerging clinical data at any time during the trial.

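### SAP 3.1 sets dose-escalation decisions at 21 days although VTE counts as a DLT for 8 (±1) weeks, and the SAP does not define the period for which DLTs are reported

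*SAP*

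**What the plan says.** **Decision point.** SAP 3.1 places the dose-escalation meeting "after all patients in each dose cohort complete the DLT evaluation period of the first 21 days of intervention". Protocol 4.1.4 has the Dose Escalation Committee (DEC) review data "immediately after all participants treated in the same dose cohort have passed the DLT period". It gives no length for that period and refers to the Dose Escalation Plan for the definition.

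**DLT windows.** The protocol synopsis states "The Dose Limiting Toxicity (DLT) period is 21 days" and, in the same sentence, that under Amendment 3 "there is an addition of a VTE-specific DLT period of 8" (±1) weeks, or until study discontinuation if sooner. Protocol 4.1.3 says that a Grade 2 VTE needing systemic anticoagulation, or any VTE of Grade 3 or higher, "regardless of investigator assessed causality, will be considered a DLT during the first 8" (±1) weeks. Table 6 gives the same window, and SAP 2.3 (Dosing) repeats it.

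**Purpose.** The mitigation column in protocol 2.3.1 lists "Extended monitoring time for VTE events to clear dose prior to dose escalation".

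**Evaluability and replacement.** Protocol 4.1.1 replaces a participant who misses too many doses "within the 21-day DLT observation period for reasons other than toxicity". Protocol 4.1.3 adds "Participants who withdraw from the study before completing 21 days of intervention for reasons other than DLT may be replaced", at the sponsor's discretion. Protocol 7.4 and SAP 14.7.1 define a DLT-evaluable participant by 21 days of intervention. None of these mentions the VTE window.

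**Reporting.** DLT incidence is a Part 1 primary endpoint (SAP 2.2). Table 3.22 and Listing 22 present DLTs during a Determinative Period, a term the SAP does not define.

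**The concern.** Amendment 3 lengthened the VTE observation window so that a dose would be judged on it. The decision point in SAP 3.1 and the evaluability rules in both documents stayed at 21 days. Followed as written, SAP 3.1 puts the escalation decision before the VTE count is complete, whereas the operating characteristics in protocol 9.2.1.1 and Table 8 treat each participant's VTE outcome as known. The first scheduled on-treatment imaging, which must include a chest CT, is at Week 9 Day 1 (protocol Table 2), also after a Day 21 review.

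Two consequences outlast the end of enrolment. First, with 21 days in SAP 3.1, 8 weeks in SAP 2.3 and the Determinative Period undefined, a programmer could apply a Day 21 cut-off and leave later VTE DLTs out of the primary safety table. Second, the SAP says repeatedly that the DEC deemed the 100 mg cohort safe, but not how much VTE follow-up lay behind that decision.

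**Working it through.** **Inputs.** The decision point is 21 days (SAP 3.1). The VTE window is 8 weeks, or 56 days, with a range of 49 to 63 (protocol 4.1.3). The rule stops a cohort at 2 or more VTEs among up to 6 participants, or 3 or more among 7–10 (protocol 9.2.1.1). The documents give no VTE onset times or accrual rate, so those are assumptions below.

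**Step 1: share of the window seen.** 21/56 = 37.5%, 21/49 = 42.9% and 21/63 = 33.3%. For the last participant enrolled, 57–67% of the window therefore lies after Day 21.

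**Step 2: reproduce Table 8.** Let K6 be the VTEs among the first 6 participants and K4 those among the next 4. A cohort of 10 is not stopped if K6 = 0 and K4 ≤ 2, or if K6 = 1 and K4 ≤ 1. At p = 0.30:

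P(not stopped) = 0.1176 × 0.9163 + 0.3025 × 0.6517 = 0.1078 + 0.1972 = 0.305, so P(stop) = 69.5%.

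| True incidence | 5% | 10% | 15% | 20% | 25% | 30% |
|---|---|---|---|---|---|---|
| Table 8 | 3.8 | 13.6 | 26.9 | 42.1 | 56.8 | 69.5 |
| Exact | 3.6 | 13.5 | 27.2 | 42.3 | 56.8 | 69.5 |

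All values agree within 0.3 points, so Table 8 is the rule applied to complete VTE outcomes.

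**Step 3: all ten at Day 21 together.** With constant hazard, the probability of a VTE by Day 21 is q = 1 − (1 − p)^(21/56). At p = 0.30, q = 1 − 0.70^0.375 = 0.125, and

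P(not stopped) = 0.4482 × 0.9929 + 0.3849 × 0.9209 = 0.4450 + 0.3544 = 0.799, so P(stop) = 20.1%.

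With a 49-day or 63-day window it is 24.8% or 16.5%. At p = 0.20, q = 0.080 and P(stop) is 9.0%, against 42.3% with complete follow-up.

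**Step 4: staggered accrual.** If one participant enters every g days and the review falls on the last participant's Day 21, participant i has been followed for t_i = min(56, 21 + (10 − i)g) days, and q_i = 1 − 0.70^(t_i/56). The event count is carried forward participant by participant, removing paths that reach the stopping limit.

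| Accrual | Follow-up, first to last (days) | Rule has fired by the review, p = 0.30 |
|---|---|---|
| All together | 21 for all | 20.1% |
| One every 3 days | 48, 45, 42, … 24, 21 | about 45% |
| One a week | 56 (first five), 49, 42, 35, 28, 21 | about 62% |
| Complete follow-up | 56 for all | 69.5% |

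**Step 5: the onset assumption.** With all ten at Day 21 together and p = 0.30, let a fraction f of the 8-week VTEs fall in the first 21 days, so that q = 0.30f. For f = 25, 50, 75 and 90%, P(stop) is 7.9, 27.2, 49.7 and 62.2%. Every value is below 69.5%, but the gap depends heavily on onset time.

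**The case against.** The strongest reply is that the protocol itself does not set a Day 21 decision. The synopsis sentence that gives 21 days also adds the VTE period, Table 6 lists VTE as a DLT over that longer window, and protocol 4.1.4 leaves the definition to the Dose Escalation Plan. That plan may name 8 weeks. This stands: the explicit 21-day timing of escalation decisions is in the SAP only. If the plan does say 8 weeks, SAP 3.1 contradicts it and still needs correcting.

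Three other replies limit the size:

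- The 20% figure needs ten participants at Day 21 on the same day. Ordinary accrual gives earlier participants longer follow-up, and first doses at uncleared doses are staggered by at least 24 hours (protocol 4.1.1).
- A VTE between Day 21 and Week 8 still counts and can still stop that dose and higher doses, and the DEC can halt enrolment at any time. What is at risk is escalation before the count is complete; the rule itself is not lost.
- The RP2D analysis in SAP 3.1 was to wait for the first post-baseline disease assessment, progression or discontinuation, so the RP2D was not to be fixed at Day 21.

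A reader might infer that someone who leaves shortly after Day 21 is counted as VTE-free and so dilutes the stopping rule. No passage says so. Protocol 7.1 keeps participants who stop treatment in the study for safety evaluation. Table 2 collects SAEs to 90 days after the last dose and includes imaging at the treatment discontinuation visit. What the documents do leave open is how the VTE count treats participants who leave the study inside the window.

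**Conclusion.** The conflict is real. SAP 3.1 contradicts the VTE DLT window in the SAP's own section 2.3 and in protocol 4.1.3, and it does not fit the purpose stated in protocol 2.3.1. At 30% true incidence and constant hazard, the chance that the rule has fired by a Day 21 review runs from about 20% to about 62% over the accrual patterns tried, against 69.5% in Table 8. These figures rest on assumed onset times and accrual.

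Two stronger readings are not supported. One is that the stopping rule's protection falls from 69.5% to 20%: that compares a worst-case snapshot with an eventual probability. The other is that 100 mg was cleared too early: the documents do not state the VTE follow-up behind that decision, so it can be neither confirmed nor excluded. Since SAP 2.1 records that no further enrolment will take place, no future escalation is at stake. The open matters are which VTE DLTs reach Table 3.22 and Listing 22, and what supports the statement about 100 mg.

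**What to change.** 1. Reconcile SAP 2.3, 3.1 and 14.7.1 with protocol 2.3.1, 4.1.1, 4.1.3, 4.1.4 and 7.4, so that the decision point, the evaluability window and the VTE DLT window agree. State what the Dose Escalation Plan specified.
2. Define the Determinative Period for Table 3.22 and Listing 22 so that a VTE DLT after Day 21 but within the VTE window is not dropped.
3. Clarify whether a VTE found on the end-of-treatment CT counts. The window closes at study discontinuation, yet protocol 4.1.3 requires that CT when a participant withdraws before the window ends.
4. Report each participant's completed VTE follow-up by dose, including the follow-up available when the DEC deemed 100 mg safe.

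The cost is wording plus one listing column. The exposure listing in SAP 8.1 already carries start and stop dates and days on treatment, but not completed VTE follow-up. With enrolment closed, no cohort is delayed, and protocol 9.6 already provides for recording changes to the planned analysis in the SAP and the clinical study report.
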